5.1.5. Trial Conduct During the COVID-19 (Coronavirus) Pandemic

The worldwide Coronavirus Disease 2019 (COVID-19) pandemic may impact the conduct of clinical studies due to the challenges from quarantines, site closures, travel limitations, and other considerations if site personnel or trial participants become potentially exposed to or infected with COVID-19. To assure the safety of trial participants, maintain compliance with Good Clinical Practice (GCP), and minimize risks to trial integrity, if necessary, in consultation with the Sponsor, the method of assessment may be changed (e.g., paper assessments replaced by electronic assessments). In addition, site visits may be replaced with telephone, internet-based video-conferencing applications, or home visits by qualified health care professionals. Normal procedures, as detailed in this protocol, will be resumed as soon as possible thereafter.

More detailed guidance on trial conduct during the COVID-19 pandemic is provided in [Appendix 6](#).

Figure 1: Trial Design

Note: if required by local regulation or if deemed necessary to assess patient safety by physical examination or after a longer follow-up period, the EOS visit may be converted to an in-person visit, and/or can occur up to Week 48.

5.2. Patient and Trial Completion

A patient is considered to have completed the trial if he/she has received the last planned dose of trial medication on Study Day 280 and completed the EOS telephone visit on Day 308.

Patients who discontinue before completing the Study Day 280 EOT visit are to attend an Early Termination visit within 14 days (± 7 days) after the last dose of trial medication for final trial assessments.

The end of the trial is defined as the date of the last visit of the last patient under the auspices of the current trial.

6. SELECTION AND WITHDRAWAL OF PATIENTS

Prospective approval of protocol deviations to recruitment and enrollment criteria (i.e., protocol waivers or exemptions) is not permitted.

6.1. Patient Inclusion Criteria

Patients must meet all of the following criteria to be eligible for trial participation:

1. Patients must have a pre-identified genetic variant in an established MC4R pathway gene that contributes to obesity

Note: Genetic testing requirements and a list of genes which have variants that are eligible for enrollment into the trial are provided in [Appendix 1](#).

2. Patients between the ages of 6 and 65, inclusive, at the time of signing Informed Consent or Assent.
3. Patients with obesity, defined as BMI ≥ 40 kg/m² for patients ≥ 18 years of age or BMI ≥ 97 th percentile for age and gender for patients 6 to < 18 years of age based on the US Centers for Disease Control and Prevention criteria.
4. Patient and/or parent or guardian is able to communicate well with the Investigator, to understand and comply with the requirements of the trial (including the QD injection regimen and all other trial procedures) and is able to understand and sign the written informed consent/assent. Patients who are unable to comply with all trial procedures due to cognitive limitations or any other reason should not be enrolled.
5. Patient must meet one of the following requirements:
Female participants of childbearing potential, defined as fertile, following menarche and until becoming post-menopausal unless permanently sterile (hysterectomy, bilateral salpingectomy, or bilateral oophorectomy), must be confirmed non-pregnant and agree to use a highly effective form of contraception throughout the trial and for 90 days following the trial.

Highly effective forms of contraception are detailed below and in Section 8.9.7:

- Combined (estrogen and progestin) hormonal contraception associated with inhibition of ovulation (i.e., oral, intravaginal, or transdermal)
- Progestin-only hormonal contraception associated with inhibition of ovulation (oral, implantable, or injectable)
- Intrauterine device (IUD)
- Intrauterine hormone-releasing system
- Bilateral tubal occlusion
- Vasectomy/vasectomized partner (provided that the vasectomized partner is the sole sexual partner of the female participant, and the vasectomized partner has received medical assessment of surgical success)
- Sexual abstinence, only if it is the preferred and usual lifestyle of the patient

Female participants of non-childbearing potential, defined as: permanently sterile (status post hysterectomy, bilateral oophorectomy, or bilateral salpingectomy), or post-menopausal for at least 12 months (and confirmed with a screening follicle-stimulating hormone level in the post-menopausal lab range) and do not require contraception during the trial.

Younger female patients who have not achieved sexual maturity at trial entry will be assessed for Tanner staging and required to comply with contraception requirements at first menarche.

Male participants with female partners of childbearing potential must agree to use a highly effective method contraception if they become sexually active during the trial or within 90 days following their participation in the trial. Male patients must also not donate sperm during and for 90 days following their participation in the trial.

6. Symptoms or behaviors of hyperphagia persistent during the patient's life, including manifestations in childhood, as determined by the Investigator at screening.

6.2. Patient Exclusion Criteria

Patients meeting any of the following criteria are not eligible for trial participation:

1. Patients with the following genetic variants: biallelic Bardet-Biedl Syndrome (BBS); biallelic Alström Syndrome 1 (ALMS1); homozygous, heterozygous, or compound heterozygous variants in MC4R, POMC, PCSK1, LEPR, nuclear receptor coactivator 1 (NCOA1; steroid receptor coactivator-1 [SRC1]) or SRC homology 2 B adapter protein 1 (SH2B1) genes as well as 16p11.2 chromosomal deletions that include the SH2B1 gene.
2. Weight loss >2% in the previous 3 months.

Patients will not be excluded for using regimens for weight maintenance or to prevent weight gain, such as dietary and/or exercise regimens, or medications, supplements or herbal treatments (e.g., orlistat, lorcaserin, phentermine, topiramate, naltrexone, bupropion, glucagon-like peptide-1 [GLP-1] receptor agonists, etc.), provided:

- the regimen and/or dose has been stable for at least 3 months prior to randomization

- the patient has not experienced weight loss >2% during the previous 3 months, AND
 - the patient intends to keep the regimen and/or dose stable throughout the course of the trial.
3. Bariatric surgery or procedure (e.g., gastric bypass/band/sleeve, duodenal switch, gastric balloon, intestinal barrier, etc.) within the last 6 months. All patients with a history of bariatric surgery or procedures must be discussed with, and receive approval from, the Sponsor prior to enrollment.
 4. Documented diagnosis of current unstable major psychiatric disorder(s) (e.g., major depressive disorder, bipolar disorder, schizophrenia, etc.) or documented worsening psychiatric condition that required changes in treatment regimen within the previous 2 years, or other psychiatric related risks that the Investigator believes may interfere with trial compliance or patient safety.
 5. Clinically significant depression or suicidality, as defined by: any suicidal ideation of type 4 or 5 on the Columbia-Suicide Severity Rating Scale (C-SSRS) during Screening, any suicide attempt during the patient's lifetime, any suicidal behavior in the last month, or a Patient Health Questionnaire-9 (PHQ-9) score of ≥ 15 during Screening process.
Note: Patients who are unable to complete the PHQ-9 or C-SSRS due to significant neurocognitive impairment may be enrolled in the trial provided that there are no clinical signs or symptoms of significant depression or suicidal behavior in the opinion of the Investigator.
 6. Current, clinically significant pulmonary, cardiac, endocrine/metabolic, hepatic, or oncologic disease considered severe enough to interfere with the trial and/or confound the results. Any patient with a potentially clinically significant disease should be reviewed with the Sponsor to determine eligibility.
 7. Significant features of, or meeting the diagnostic criteria for, a genetic syndrome that is associated with obesity.
Note: Although some of the genetic variants that are eligible to be enrolled into this trial are associated with specific syndromes, the intent of this trial is not to enroll children with significant cognitive impairment or other significant co-morbidities. Patients with eligible genetic variants, but who otherwise do not exhibit the syndrome, are eligible for enrollment.
 8. HbA_{1C} >10.0% at Screening.
 9. History of significant liver disease other than non-alcoholic fatty liver disease (NAFLD) or nonalcoholic steatohepatitis (NASH). Patients with NAFLD or NASH will not be excluded based on this criterion
 10. Estimated glomerular filtration rate (eGFR) <30 mL/min/1.73 m² at Screening. In patients ≥ 18 years of age the Modification of Diet in Renal Disease (MDRD) Equation should be used to calculate eGFR. In patients <18 years of age, the Bedside Schwartz Equation should be used for calculation of GFR.
 11. History or close family history (parents or siblings) of melanoma, or patient history of oculocutaneous albinism.

Note: If the type of skin cancer in patient's or close family history is not known, then the patient should not be enrolled into the trial.

12. Significant dermatologic findings relating to melanoma or pre-melanoma skin lesions (excluding non-invasive basal or squamous cell lesion), determined as part of a comprehensive skin evaluation performed by the Investigator during Screening. If any concerning lesions are identified during Screening, the patient should be referred to a dermatologist. Any concerning lesions identified during Screening will be biopsied and results known to be benign prior to enrollment. If the pre-treatment biopsy results are of concern, the patient may need to be excluded from the trial.
13. Patient is, in the opinion of the Investigator, not suitable to participate in the trial.
14. Participation in any clinical trial with an investigational drug/device within 3 months or 5 half-lives, whichever is longer, prior to the first day of dosing.
15. Patients previously enrolled in a clinical trial involving setmelanotide or any previous exposure to setmelanotide.
16. Hypersensitivity to the active substance or to any of the excipients of the investigational medicinal products (active and placebo).
17. Females who are pregnant or breastfeeding, or planning or desiring to become pregnant during the duration of the trial.
18. Legally protected persons per local regulations (e.g., those that fall under the L1121-6 article of the Public Health code in France).
19. For France only: patient is <18 years of age.

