5. INVESTIGATIONAL PLAN

5.1. Overall Trial Design

This is a 2-stage (open-label stage followed by a randomized, double-blind, placebo-controlled stage) Phase 2 trial of setmelanotide in patients with obesity with specific gene variants in the MC4R pathway. Approximately 100 patients between the ages of 6 and 65 years, inclusive, are planned to be enrolled in Stage 2 of the trial with up to 200 patients enrolled in Stage 1 (open-label). The trial design is depicted in [Figure 1](#).

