5.1.2. Stage 1 (Open-Label)

Stage 1 of the trial begins with the Enrollment Visit (Study Day 1). During the Enrollment Visit, patients will undergo all procedures as outlined in the SoA Stage 1 (Table 1) and it will be reconfirmed that the patient continues to meet the Inclusion and Exclusion criteria. At the Enrollment Visit, the trial center must confirm that the patient completed the electronic diary at least 4 of 7 days prior to the Enrollment Visit. If the diary was not appropriately completed, the patient may not enter the trial. The Enrollment Visit may be re-scheduled if the remaining visit window allows.

During the Enrollment Visit, the patient will have their body weight recorded. This will be the patient's "Baseline Weight." During the Enrollment Visit, the patient (or caregiver) will receive training on injections of trial medication and will administer the first dose of setmelanotide under the supervision of the trial staff. In-clinic doses of trial medication, including the first dose, will be administered following blood sampling for pharmacokinetic (PK) analysis.

During Stage 1, the patient (or caregiver) will administer setmelanotide on a daily basis for 16 weeks. During this period, the patient will have in-person as well as virtual visits using a validated Telehealth platform with the trial center. During the virtual visits, the patient (or caregiver) will record a body weight measurement and be assessed for compliance with trial procedures and AEs. Any visit that is planned as a virtual visit may be converted to an in-person visit at the discretion of the Investigator. If more than 2 virtual visits are to be converted into in-person visits, Sponsor approval is required.

To be eligible to enter Stage 2 of the trial, a patient

- ≥ 18 years old must have achieved a body mass index (BMI) at least 3% less than the Baseline BMI at the end of Stage 1
- < 18 years old must have achieved a BMI at least 3% less than the Baseline BMI or a decrease in BMI Z-score of at least 0.05 at the end of Stage 1

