If the patient completed the full 16 weeks of Stage 1 and at the Day 112 visit (Week 16) the patient has not achieved the required change in BMI or BMI Z-score (for patients < 18 years) since the Baseline Visit, instead of the Stage 2 Entry Visit, the site will perform the End-of-Treatment (EOT) Visit for this patient. These patients will end treatment with setmelanotide and continue to be monitored for resolution of any ongoing serious adverse events (SAEs) with virtual visits once every 4 weeks until all SAEs have resolved.

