7.2. Randomization, Blinding, and Unblinding

7.2.1. Stage 1

Stage 1 of the trial is open-label, and all patients will receive setmelanotide.

7.2.2. Stage 2

Patients who are eligible to enter Stage 2 of the trial will be randomized in a blinded manner on Day 112 (Stage 2 Entry Visit) in a 2:1 ratio to receive either setmelanotide (2) or placebo (1). The randomization schedule will be generated by the Sponsor or its designee, and trial personnel will use a web-based interactive response technology (IRT) system to obtain the randomization number for each eligible patient.

Stage 2 of this trial is double-blinded. The patient, Investigator, and Sponsor will be blinded to trial treatment.

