7.7. Concomitant Medications

Medication that is considered necessary for the patient's safety and wellbeing may be given during the trial at the discretion of the treating physician after discussion with the Medical Monitor.

All concomitant medications should be kept at a stable dose throughout the course of the trial unless a dose change is necessary due to an AE.

Any medication or vaccine (including over-the-counter or prescription medicines, vitamins, and/or herbal supplements) that the patient is receiving at the time of enrollment or receives during the trial must be recorded along with:

- Reason for use
- Dates of administration including start and end dates
- Dosage information including dose and frequency

GLP-1 receptor agonists and anti-obesity medications may be used as long as:

- the regimen and/or dose has been stable for at least 3 months prior to randomization
- the patient has not experienced weight loss $\geq 2\%$ during the previous 3 months, AND
- the patient intends to keep the regimen and/or dose stable throughout the course of the trial.

The Sponsor should be contacted if there are any questions regarding concomitant or prior therapy.

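### The 3-month stability rule for background weight regimens is counted back from randomization (Day 112), so it cannot be verified when eligibility is decided at Screening and Day 1

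*Protocol*

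**What the plan says.** Exclusion criterion 2 in Protocol 6.2 exempts patients on "regimens for weight maintenance or to prevent weight gain" under three conditions: "the regimen and/or dose has been stable for at least 3 months prior to randomization"; no weight loss above 2% in the previous 3 months; and an intention to keep the regimen stable for the rest of the trial. The Synopsis repeats this. Section 7.7 has the same time anchor under the lead-in "GLP-1 receptor agonists and anti-obesity medications may be used as long as". It does not carry the maintenance limit, and it sets the weight-loss limit at 2% or more, not above 2%.

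Protocol 7.2.2 says that eligible patients "will be randomized in a blinded manner on Day 112 (Stage 2 Entry Visit"). There is no other randomization. At the Enrollment Visit on Day 1, Protocol 5.1.2 says "it will be reconfirmed that the patient continues to meet the Inclusion and Exclusion criteria". Table 1 marks the inclusion/exclusion review at Screening and at that visit only. The Stage 2 entry conditions in 5.1.2 are stated only as BMI or BMI Z-score change. For a patient who completes Stage 1 but misses them, "instead of the Stage 2 Entry Visit, the site will perform the End-of-Treatment (EOT) Visit for this patient".

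Other entry rules use an entry anchor. Exclusion 14 counts back from the first dosing day, and exclusion 3 requires Sponsor approval before enrollment.

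**The concern.** A stability requirement is meant to ensure that a background drug has reached its steady effect before Baseline, so that later change is not due to that drug. Counted from Day 112, the requirement says nothing about the time before Baseline. Sites must either apply a condition that lies in the future or substitute their own anchor, and about 80 centers may not choose the same one. Protocol 6 leaves no room for case-by-case relief: "Prospective approval of protocol deviations to recruitment and enrollment criteria" is ruled out.

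Stage 1 has no control group, and its primary endpoint is a BMI reduction of at least 5% from Baseline to Week 16. If a recently started background drug goes on lowering weight after Day 1, that loss is credited to setmelanotide. The visible estimand (SAP II.A) addresses treatment discontinuation and rescue medication only, both by treatment policy. SAP IX.G tabulates prior and concomitant medications, and SAP VI.D lists weight-loss interventions and medication history. Nothing in the visible text relates the start date of such a drug to response.

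**Working it through.** **Inputs**
- Randomization: Day 112 (Protocol 7.2.2). Visit 7 window ±5 days (Table 1), so Day 107-117.
- Screening: Day -56 to Day -14 (Table 1), starting with consent (Synopsis).
- Study-day convention: no Day 0 (SAP V.D). Day -14 is 14 days before Day 1, and Day 112 is 111 days after it.
- Length of 3 months: not defined in days. Assumed 89-92 days (three calendar months).

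**The plan's own figure.** 16 weeks × 7 = 112, which agrees with Day 112.

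**Where the look-back opens** (randomization day minus 89-92)
- Day 112: 112 - 92 = Day 20, to 112 - 89 = Day 23.
- Across the visit window: 107 - 92 = Day 15, to 117 - 89 = Day 28.
- If 3 months is read as 12 weeks (84 days): 112 - 84 = Day 28 (Day 23-33 across the window), later still.

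No day of the look-back falls on or before Day 1. To reach Day 1, randomization would have to take place by Day 1 + 89 = 90 to 1 + 92 = 93. The earliest Visit 7 is Day 107.

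**A fixed-dose drug begun just before consent**
- Use at Day 1: 14 to 56 days.
- Use at Day 112: 14 + 111 = 125 to 56 + 111 = 167 days. If Visit 7 falls on Day 107, the minimum is 14 + 106 = 120 days. All exceed 92, so the stability condition is met.
- Shortfall if counted from Day 1, with 3 months = 91 days: 91 - 56 = 35 to 91 - 14 = 77 days (33 to 78 with 89-92 days). The same drug would fail.

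**What the other conditions catch**
- The 2% limit removes patients who have already lost more than that by Day 1. It does not touch an effect that appears later.
- The intention to stay stable rules out a planned titration. It does not rule out a continuing effect at a fixed dose.
- The maintenance wording in 6.2 narrows the class of regimen. Section 7.7 has no such limit.

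**Patients never randomized.** A patient on such a regimen who misses the Stage 2 gate has no date from which to count. Missing the gate means a BMI reduction below 3%, for adults and for those under 18, and so below 5%: a primary non-responder. A patient with no usable Week 16 BMI is also a non-responder (SAP V.E). The exceptions are a patient who met the gate but was not randomized, and an early leaver whose weight maps into the Week 16 window.

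**The case against.** The strongest reply is that nobody would read the rule literally. It is an entry criterion, reviewed only at Screening and Day 1, and exclusion 14 shows what was meant. If the adjacent 2% weight-loss condition were also read at randomization, it would clash with the adult Stage 2 gate, which requires a BMI at least 3% below Baseline. Section 7.7 tells sites to contact the Sponsor with questions on prior or concomitant therapy, and exclusion 13 lets the investigator exclude an unsuitable patient. Medication use and previous weight-loss efforts are collected at Screening (8.3), and SAP VI.D lists weight-loss interventions with dates, so recent starters should largely be identifiable. The analysis is descriptive (SAP V.K), and Stage 1 response is already mixed with the effect of counselling to cut 500-750 kcal per day (6.5.2).

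Most of this stands. The wording is probably a slip, and some sites will have applied it as enrollment. But no visible text re-anchors the rule, identical words appear in three places, and a listing does not show how the response rate changes without recent starters.

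Two stronger readings are tempting and are not supported. First, a reader might infer from the planned totals (about 100 patients "are planned to be enrolled in Stage 2 of the trial with up to 200 patients enrolled in Stage 1 (open-label")) that half the trial lacks a reference date. The rule concerns only patients on a background regimen, whose number is not given, and 200 is a ceiling. Second, a reader might infer that undated patients inflate the response rate. Those who miss the gate are non-responders by definition, so the missing date is a problem in applying the rule, not a source of false responders.

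**Conclusion.** The point holds as a defect in an entry criterion. As written, the stability condition cannot be verified when it is applied, covers no time before Baseline, and has no date for regimen users who are never randomized. The arithmetic rests only on the visit schedule and on reading 3 months as 84-92 days, and the conclusion is the same across that range.

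The consequence for the primary endpoint is narrow. It needs a fixed-dose weight-maintenance drug begun shortly before consent, a loss of no more than 2% by Day 1, enough later effect to carry the patient past 5%, and a site that applies the text literally. The documents give no figure for any of these, so neither the number of patients nor the bias can be stated. A reader might infer that the Stage 1 response rates are materially biased; the documents do not show that. Two limits apply: parts of Table 2 are redacted, so the absence of a stability check at Visit 7 rests on Table 1 and the stated Stage 2 conditions; and much of the SAP efficacy text is redacted and may already hold a relevant analysis. The change is worth making because it is small and removes an avoidable ambiguity.

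**What to change.** 1. In Synopsis exclusion 2, Section 6.2 exclusion 2 and Section 7.7, change the anchor of the 3-month stability condition from randomization to the Enrollment Visit (Day 1), consistent with the first-dose anchor of exclusion 14.
2. In the same amendment, reconcile the weight-loss limit, which is above 2% in 6.2 and the Synopsis but 2% or more in 7.7.
3. For patients already enrolled, unless the redacted SAP text already provides it, add one sensitivity table of the primary endpoint that excludes patients whose recorded weight-loss medication or regimen started or changed within 3 months before Day 1. Use the start dates recorded under Protocol 7.7 and in the SAP VI.D listings, not imputed ones: SAP V.E can set a partial start date to the first-dose date, which would make a long-term user look like a recent starter. List separately the patients whose start cannot be dated.

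Cost: one phrase in three places plus the limit, but as a protocol amendment it needs IRB/IEC approval (Appendix 7) across about 80 centers, and it helps only patients not yet enrolled. A few recent starters would wait or be screened out. The table needs no new data collection.
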